8.1 Stopping Rules for Subjects

- A single episode of severe gastrointestinal discomfort that in consultation with the physician is severe enough to discontinue the protocol
- Moderate gastrointestinal symptoms that persists for more than 5 consecutive days relating to the supplementation and as determined by contact with the investigator
- Pregnancy and breastfeeding
- Anaphylactic reaction due to consumption of the fish oil supplement

- New onset atrial fibrillation/flutter
- Major bleeding episode (CTCAE 4.0 grade III or IV)
- Subjects taking irregular use of fish oil capsules that in the opinion of the PI may compromise the data integrity.
 - Any other severe symptoms related to the study and as determined by contact with the physician.

Subjects who are found to be pregnant or wish to breastfeed during the study will automatically be withdrawn. A pregnancy screening will be done for all female volunteers at the first visit and subjects will be excluded from the study if pregnant. It is not known whether the oils used in this study are secreted in breast milk. It is therefore not advisable for any breastfeeding woman to participate in this study. However, if a subject becomes pregnant during this study, monitoring of the pregnancy will continue until conclusion of the pregnancy.

Unlikely but possible adverse effects of omega-3 supplements may include atrial fibrillation (risk less than one in a hundred persons). Patients that develop symptoms of atrial fibrillation (palpitations, rapid heart rate, fainting, shortness of breath, etc.) will be instructed to visit the emergency room and seek treatment immediately. In order to prevent any future events, participants with atrial fibrillation will be withdrawn from the study. Individuals that develop an allergy to fish or shellfish may experience an anaphylactic reaction from the supplement and will also be instructed to visit the emergency room immediately and will also be withdrawn from the study (risk believed to be less than one in a thousand persons not known to have fish or shellfish allergy).

9. Analysis of the Study

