Accrual and safety data will be monitored and reviewed annually by the Institutional Review Board (IRB). Prior to implementation of this study, the protocol and the proposed patient informed consent document will be reviewed and approved by the properly constituted IRB operating according to the 45 CFR 46 Code of Federal regulations. This committee must approve all amendments to the protocol or informed consent document, and conduct continuing annual review so long as the protocol is open to accrual or follow up of subjects.

FDA: An annual progress report, any amendments to the protocol, and any change in the status of the protocol will be forwarded to the FDA in compliance with 21CFR 312.33

14. Compensation

Compensation will be provided to the subjects for their time and inconvenience of participating on this protocol based on the values listed below:

| Procedures | Inconvenience Unit | \$ | Frequency | Total \$\$ |
|--|--------------------|------|-----------|--------------|
| Outpatient Visit (first hour) | 2 | \$20 | Up to 8 | \$160 |
| Outpatient Visit (additional hours, up to 4 hours) | 1(per hour) | \$10 | Up to 8 | \$320 |
| Physical Examination | 1 | \$10 | Up to 8 | \$80 |
| Screening Blood Draw | 1 | \$10 | Up to 3 | \$30 |
| Research Blood Draw | 1 | \$10 | Up to 6 | \$60 |
| Stool Sample (optional) | 1 | \$10 | Up to 4 | \$40 |
| Diet & Exercise Assessment | 1 | \$10 | Up to 6 | \$60 |
| CAVI | 2 | \$20 | Up to 6 | \$120 |
| EKG (Electrocardiogram), General | 1 | \$10 | Up to 2 | \$20 |
| Total potential compensation: | | | | \$890 |

Subjects will receive full compensation only after completing the entire study. Subjects that fail to complete the study for any reason will not receive compensation.

15. References

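### Section 14 withholds all payment from any subject who does not finish, including one withdrawn for an adverse event, which gives subjects a reason to under-report symptoms

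*Combined protocol and SAP*

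**What the plan says.** Section 14 gives the purpose of payment: "Compensation will be provided to the subjects for their time and inconvenience of participating on this protocol". A table then assigns a dollar value to each visit hour, examination, blood draw and test, adding up to $890.

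Two sentences follow the table. The first is "Subjects will receive full compensation only after completing the entire study", which alone might leave room for part payment. The second closes that room: "Subjects that fail to complete the study for any reason will not receive compensation".

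Section 8.1 lists the grounds for stopping a subject. Three matter here:

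- "Moderate gastrointestinal symptoms that persists for more than 5 consecutive days relating to the supplementation and as determined by contact with the investigator"
- "Subjects taking irregular use of fish oil capsules that in the opinion of the PI may compromise the data integrity"
- new atrial fibrillation or flutter, of which the text says "participants with atrial fibrillation will be withdrawn from the study"

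Section 10.6 goes further than Section 8.1 on cardiac symptoms: a subject with palpitations, rapid heart rate or shortness of breath is sent to the emergency room and withdrawn. Section 12.1 expects subjects to report adverse events up to 30 days after the last dose. Section 10.8 lets subjects withdraw consent at any time.

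**The concern.** The payment rule and the safety rules pull in opposite directions. Persistent moderate gastrointestinal symptoms, palpitations and missed capsules come to light mainly because the subject mentions them. Mentioning them can end participation, and ending participation cancels payment for work already done. The subject therefore has a financial reason to say less.

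Two kinds of data are exposed. Adverse event counts may be too low in absolute terms, and some subjects may stay on supplement when a stopping rule would have applied. Pill counts may look better than true intake, because unused capsules can be thrown away before the visit.

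The rule also sits badly with its own stated purpose. A subject withdrawn after Visit 3 has borne most of the time and inconvenience and receives nothing.

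**Working it through.** **1. The plan's own total.** Unit payment times maximum frequency, from the Section 14 table:

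| Item | Calculation | Total |
|---|---|---|
| First hour of visit | $20 × 8 | $160 |
| Additional hours | $10 × 4 h × 8 | $320 |
| Physical examination | $10 × 8 | $80 |
| Screening blood draw | $10 × 3 | $30 |
| Research blood draw | $10 × 6 | $60 |
| Stool sample | $10 × 4 | $40 |
| Diet and exercise assessment | $10 × 6 | $60 |
| CAVI | $20 × 6 | $120 |
| EKG | $10 × 2 | $20 |
| **Sum** | | **$890** |

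Every row and the total reproduce. The figure assumes up to eight visits, whereas Section 3.2 plans four.

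**2. What is earned on the planned schedule.** The documents do not say how many hours or optional tests each visit involves, so I bracket them.

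- Low case: no additional hours, physical examination at Visit 1 only, no stool sample, no CAVI, diet assessment at Visits 1 and 2 only.
- High case: four additional hours and every listed procedure at each visit.
- Both cases: one screening draw and one EKG, both at Visit 1, and a research draw at every visit.

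Low case, by visit:

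- Visit 1: 20 + 10 (examination) + 10 (screening) + 10 (research) + 10 (diet) + 10 (EKG) = $70
- Visit 2: 20 + 10 (research) + 10 (diet) = $40
- Visits 3 and 4: 20 + 10 (research) = $30 each

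High case, by visit:

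- Visit 1: 20 + 40 (hours) + 10 (examination) + 10 (screening) + 10 (research) + 10 (stool) + 10 (diet) + 20 (CAVI) + 10 (EKG) = $140
- Visits 2 to 4: 20 + 40 + 10 + 10 + 10 + 10 + 20 = $120 each

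| Last visit completed | Earned to date | Paid under Section 14 |
|---|---|---|
| 1 | $70 to $140 | $0 |
| 2 | $110 to $260 | $0 |
| 3 | $140 to $380 | $0 |
| 4 | $170 to $500 | $170 to $500 |

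Every non-completer loses 100% of what has been earned, and the sum grows with time. A subject taking supplement has last completed Visit 1 (first period) or Visit 3 (second period), so the earned sums at stake during dosing are $70 to $140 and $140 to $380.

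**3. Which reports are exposed.** Visits are at least eight weeks apart (Section 3.2), and telephone or email contact between them is optional (Section 3.1). Section 3.2 names an EKG only at Visit 1, although Section 6 lists it among tests that may be used. Between visits, gastrointestinal and palpitation-type symptoms are therefore known mainly through the subject.

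**4. Which adherence data are exposed.** Pill counts are taken at Visits 2 and 4 (Section 3.1). The definition of an evaluable subject in Section 9.1 does not use them. It requires completion of the timeline, stool collection, and red-cell omega-3 results showing that the supplement was taken and absorbed. Discarding capsules does not change red-cell fatty acids. Section 9.1 gives no cut-off, however, so partial non-adherence could still pass.

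**The case against.** The case against giving this much weight has several parts.

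- **Most reports cost nothing.** Under Section 8.1, gastrointestinal symptoms stop a subject only if severe enough in consultation with the physician, or if moderate, related to the supplement and lasting more than five consecutive days. Irregular capsule use counts only if the PI thinks data integrity may suffer. Pregnancy is tested at every visit, and anaphylaxis or major bleeding is hard to hide. This stands, and it narrows the exposure to persistent gastrointestinal symptoms, palpitation-type symptoms and substantial missed dosing.
- **Adherence has an objective check.** This largely stands. A reader might infer that the rule corrupts the evaluable set or dilutes the treatment contrast through false pill counts. The documents do not support that, since pill counts are not part of the evaluable definition and Section 9.2 does not use them.
- **No differential effect.** A reader might infer a biased safety comparison. Subjects are blinded and the same rule covers both supplements. If concealment is equally likely on each, both counts fall by the same fraction. No mechanism for a difference appears in the documents, and Section 9 plans no formal safety comparison.
- **Pro-rata payment leaves some incentive.** After Visit 1, the visits still to come are worth $100 to $360 (170 − 70 and 500 − 140). After Visit 3, the last visit is worth $30 to $120. What the forfeiture rule adds is the earned money.
- **It is late, and payment belongs to IRB and consent review.** Section 10.6 says accrual is closed and only analysis continues, so collected data cannot change. The rule still affects how those data should be read and what a later trial copies.

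**Conclusion.** The point holds in a limited form. Read as written, Section 14 cancels payment for completed procedures whenever a subject does not finish, with no exception for withdrawal on safety grounds. That gives subjects a reason to under-report the symptoms on which some stopping rules depend. Symptom reporting is the main concern. Pill counts are secondary because red-cell fatty acids provide an independent check.

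The earned amount lost is about $70 to $140, $110 to $260 or $140 to $380 after Visits 1, 2 and 3, on the bracketing assumptions above. A reader might take $890 as the sum at risk at any time, but that is a ceiling for up to eight visits, and a completer of the four planned visits earns about $170 to $500.

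A reader might also conclude that adverse events were in fact under-reported. The documents contain no data on concealment, so the effect on reporting is an inference of unknown size. Consent pages were not available, so different payment wording there can be neither excluded nor assumed.

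**What to change.** Change Section 14, and the consent form where it matches, in three ways:

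- Pay for each visit and procedure completed, at the unit rates already in the table.
- State that withdrawal for an adverse event or under a stopping rule does not forfeit payment earned.
- If a completion payment is kept, make it a small, separate item.

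Because accrual is closed, the present steps are:

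- Pay withdrawn subjects for completed procedures at those rates.
- Report the number of non-completers, with the reason and the last visit completed for each.
- State beside the adverse event and pill-count summaries that these data were collected under a forfeiture rule, so absolute event counts may be low.
- Keep the rule out of the larger trial that this pilot is meant to inform.

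The cost is a wording change, small pro-rated payments (up to about $380 per non-completer on the planned schedule) and a slightly weaker incentive to complete.
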